5.7 END OF ESSAY

The end of the trial will be considered the day of the final visit of the last patient included in the study.

6 PATIENT SELECTION AND WITHDRAWAL

6.1 INCLUSION CRITERIA.

Patients older than or equal to 65 years of age who are going to undergo major non-cardiac surgery and who have a score equal to or greater than 5 on the Delphi scale:

- Age: 70-79 years: 1 point; >80 years: 2 points.
- Physical activity: need for assistance, not self-sufficient: 2 pointss
- Alcoholism: 1 point.
- Hearing deficit: 1 point.
- History of delirium: 2 points.
- Urgent surgery: 1 point.
- Non-laparoscopic surgery: 2 points.
- Admission to Critical Units: 3 points.
- C-Reactive Protein (CRP) value > 10 mg/dL: 1 point.

6.2 EXCLUSION CRITERIA.

- × the lergia the quetiapine.
- × lactose intolerance.
- × patients with a score of less than 5 on the Delphi scale.
- × Diagnosis of delirium on admission.
- Cardiological diseases: QTc >460 msec in men, >470 msec in women, AMI or recent cardiac decompensation, AV block 2-3° or history of torsades de pointes arrhythmias or ventricular arrhythmias, bradycardia (<45 bpm).
- × hipopotasemia <3 mEq/CLK.
- × history of drug use.
- × Patients on antipsychotic or antidopaminergic treatment (chlorpromazine, clozapine, olanzapine, risperidone, haloperidol, quetiapine, paliperidone, amisulpride).
- × Parkinson's disease.
- × Minimental < 24.
- × vascular dementia or Levi's bodies.
- × Disorder of movements hipokinéticos.
- × History of neuroleptic malignant syndrome.
- × Central anticholinergic syndrome.
- × epilepsy.
- × patients weighing less than 50 or more than 200 kg.

× Patients participating in or having participated in a study of an investigational drug or device within four weeks prior to administration of the first dose of study treatment.

6.3 NUMBER OF PATIENTS.

Taking into account the current published literature, the estimated incidence of delirium in this type of population is 20-25%(2). We consider that a reduction in the absolute risk of delirium of 12% is clinically relevant , being similar to the reduction of absolute risk with non-pharmacological measures (10). Therefore, a sample size of 350 patients is estimated, with 175 subjects per treatment branch (significance level 95%, power 80%, expected losses of 5%).

6.4 EXPECTED CRITERIA FOR WITHDRAWAL OF STUDY SUBJECTS.

- 1. Voluntary patient abandonment: patients have the right to withdraw from the study at any time and for any reason, being able to express it personally or through their representative.
- 2. By medical criteria (safety and efficacy):
 - a. Admission to critical care units for postoperative complications.
 - b. Significant prolongation of the QTc interval: prolongation greater than 60 miliseconds or QTc greater than 500 msec (1.28) during the study or appearance of ventricular tachycardias / torsades de pointes.
 - c. When, for any reason, the treatment is no longer safe for the patient (for example, the patient has an allergic reaction to it), it may aggravate his disease, endanger his life or have serious consequences for him.
- 3. For non-compliance or violation of the rules contained in the protocol: when the patient no longer complies with the rules or proceduresestablished in this protocol or there is loss of follow-up.

6.5 FOLLOW-UP OF STUDY PATIENTS.

The monitoring of the pacientis will be done from the signing of the informed consent (CI) until the last view marked by protocol. In the case of retired patients, follow-up will be done until the date of withdrawal that will be documented in the clinical history with the reason for it, whenever possible, and a premature withdrawal visit will be made.

6.6 PREMATURE DISCONTINUATION OF THE STUDY.

This study may be stopped prematurely if in the opinion of the sponsor or regulatory authorities there is sufficient reasonable cause. The investigator will receive written notice that the terminating party documents the reason for the suspension of the study.

The circumstances justifying the suspension of the present study include, but are not limited to:

- a) Identification of unforeseen, significant or unacceptable risks to patients.
- b) Inability to enroll an acceptable number of patients.
- c) Insufficient compliance with protocol requirements.
- d) Plans for modification, suspension or discontinuation of study drug development.
- e) Administrative reasons that the promoter could not solve with the health authorities.

If the trial ends early or is suspended for any reason, the investigator shall promptly inform the trial subjects, ensuring appropriate treatment and follow-up of the trial and, where required by applicable law, inform the regulatory authority.

If the investigator terminates or suspends a trial without the prior agreement of the sponsor, he or she shall promptly inform the institution, and the investigator/institution shall promptly inform thesponsor and the CEIm and provide them with written justification of the cause of such termination or suspension.

If the sponsor terminates or suspends a trial, the investigator must inform the institution where the trial is conducted and the investigator/institutionmust promptly inform the CEIm by providing written justification of the reasons for the termination or suspension.

If the Ethics Committee (CEIm) terminates or withdraws the favourable opinion of a trial, the investigator shall inform the institution and the investigator/institution shall promptly inform the sponsor and provide written justification for the cause oftermination or suspension.

7 PATIENT TREATMENT.

7.1 CLINICALTRIAL MATERIALS.

The active drugwill be supplied by the promoter (IBSAL).

The manufacture of the medication will be entrusted to an independent company (LABORATORIUM SANITATIS, S.L.) which will generate identical capsules for active drugs and placebo under rules of good manufacture of medication according to current legislation. Subsequently, they will be sent to the pharmacy service of the C.A.U.S.A. Theperson in charge of dispensing the medication will be the only one who knows if the treatment is the active drug or is the placebo. All the medication that the patient will receive together will be dispensed, in a bottle containing the 6 corresponding capsules. The treating physician will leave reflected in the treatment orders: administrar quetiapine/placebo 1 capsule orally every 12 hours. The first dose of active drug/placebo will be administered 60 minutes after arrival at the resuscitation unit and every 12 hours thereafter for the first 3 postoperative days.

7.2 SCHEDULE OF VISITS AND PROCEDURES.

See Figure 1: Outline procedures in each visit.

- I. Pre-selection visit: where the patient is selected by assessing the inclusion and exclusion criteria. Itwill explain what the clinical trial consists of and give youthe documentation (information sheet and informed consent).
- II. Selection visit: it will be carried out during the pre-anesthesia consultation or the day before the surgical intervention. Thefollowing procedures shall be carried out:
 - signature of CI.
 - Verification of compliance with selection criteria.

- Demographics.
- Relevant medical history: Preoperative comorbidity.
- ASA classification.
- Preoperative medication: sleep medication, antidepressants, opiates, corticosteroids...
- vital signs.
- complete analysis with PCR.
- previous physical function: independent for activities of daily living (Barthel index).
- Basal cognitive function (valued with MINIMental o 6 ICT).
- CAM scale.
- ECG and QTc measurement.
- III. Postoperative visits: A daily personal clinical visit will be made to all randomized patients during the first four days of the postoperative period or during the duration of their admission if it is less than 4 days. In this case, the last visit during admission will be the visit to discharge.

These clinical visits will be listed in corresponding to the postoperative day: visit 1st day post, visit 2nd day post... so on until the 4th postoperative day.

Procedures to be performed:

- CAM scale.
- RASS scale.
- Extrapyramidal symptoms.
- vital signs.
- ECG and QTc measurement (after administration of the 4th dose).
- Complete laboratory tests (at least one during the first four days after surgery).
- VAS scale and analgesia received (opiates).

In addition, during the 1st postoperative visit, the intraoperative variables will be collected:

- Type of surgical intervention and specialty.
- urgent ly programmed.
- anesthetic technique performed.
- Drugs used, doses and routes of administration(benzodiazepines, opiates, glucocorticoids, atropine).
- Measurement of anesthetic depth and/or regional brain oxygen saturation where possible.
- Duration anesthesia .
- EVA upon admission to URPA/Resuscitation.
- Analgesia: IV or by regional techniques(drug used, dose and administration).
- blood transfusion.

If the patient develops delirium, the daily visit will continue until the clinic disappears. In this case, the following will also be collected:

- severity of the picture using DRS scale -R- 98
- Drug used for its treatment, dose and route of administration.

- IV. Discharge visit: when the patient meets criteria and is discharged. The following will be collected:
 - Reason for hospital discharge.
 - CAM.
 - RASS.
 - vital signs.
 - Extrapyramidal symptoms.
 - Hospital evolution including complications that have appeared and that have required medical treatment (≥ grade II Clavien-Dindo scale): blood transfusion, surgical reoperation, pneumonia
 - mortality.
 - complete anal itatic if it has not been collected in the postoperative visits.
 - If you have developed delirium:
 - × duration.
 - × Severity.
 - × Dosage and route of administration of the drug used for its treatment.
 - V. Premature withdrawal visit: all patients who, regardless of the cause and phase of the study in which they are, prematurely and permanently stop treatment, must complete the premature withdrawal visit, which will take place in the following 24-48 hours from the time the withdrawal is known. During the same the following procedures will be carried out:
 - reason de premature interruption.
 - vital signs.
 - CAM.
 - RASS.
 - sextrapyramidal symptoms.
 - Hospital evolution including complications that have appeared and that have required medical treatment (≥ grade II Clavien-Dindo scale): blood transfusion, surgical reoperation, pneumonia
 - if you have developed delirium:
 - × duration.
 - × severity.
 - × Dosage and route of administration of the drug used for its treatment.
- VI. Final visit: It will be carried out at 28± 2 days from the start of treatment. A personal, telephone or mail follow-up will be carried out to determine the vital status (mortality) and quality of life in relation to health through the SF 36 questionnaire. Complications that have appeared during this period and that have required medical treatment (≥ grade II Clavien-Dindo scale) will also be collected.

	VISITAS								
	Preselección	Selección	1-post	2-post	3-post	4-post	Alta	Final (28± 2 días)	Retirada prematura
Criterios de selección	х	х							
Entrega de	×								
documentación	X								
Firma Cl		х							
Variables		Y							
demográficas		X							
Comorbilidad		х							
ASA		х							
Medicación		Y							
preoperatoria		X							
CAM		х	х	х	х	х	х		x
BARTHEL		х							
MINIMETNTAL		х							
ECG con QTc		х			х				
RASS			х	х	х	х	х		x
Constantes vitales		х	х	х	х	х	х		х
Síntomas			v	v	v	v	v		v
extrapiramidales			X	X	X	X	X		X
Variables									
intraoperatorias			X						
EVA y analgesia			х	х	х	х			
Complicaciones no									
relacionadas con							х	x	x
delirio									
Mortalidad							х	х	
SF-36								х	
Datos analíticos		х	x*	x*	x*	x*	х		
Severidad del delirio			х	х	х	х	х		х
Tratamiento del delirio			x	x	x	x	x		x
Duración del delirio							х		х

Figure 1: Outline procedures in each visit. * At least one complete analysis during the period of admission.

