8 N-ASSESSMENTOF EFFECTIVENESS

8.1 EFFICACY VARIABLES.

The efficacy of the treatment is given by the main variable: incidence of delirium during the postoperative period in the first 4 days in both intervention groups.

The secondary variables will be collected: number of days free of delirium, duration and severity of delirium if it finally develops; hospital stay, adverse effects, mortality at discharge and 28 ± 2 days, perceived quality of life at 28 ± 2 days.

8.2 EVALUATION METHODS.

To obtain the main variable we will use the CAM scale (Confusion Assessment Method) as a method of diagnosis of the appearance of delirium. It is a scale based on the DSM IV definition of delirium (29) and with demonstrated internal and external validity for surgical patients (17,24-27). It consists of an interview of the clinician consisting of six items: two addressed to the closest caregiver (family member or nursing technician) with which information is obtained on the beginning of the picture and the presence of fluctuations. The remaining four items are to ask the patient, to determine their cognitive impairment that evaluates attention, thinking and consciousness. In the second part of the instrument, the clinician answers a questionnaire of 4 questions (yes / no), based on the evaluation made. The diagnosis of delirium is established around the presence of its two fundamental criteria (abrupt onset with fluctuations of symptoms and loss of attention) and one of the two secondary criteria (disorganized thinking and altered level of consciousness). We will use the same scale to rule out the presence of delirium in the initial assessment of the patient and to determine the duration of the picture during the follow-up period. The assessment of the response will be carried out daily in both study groups, during the first 4 days of admission or until the patient's discharge.

We will use the RASS scale (Richmond Agitation sedation scale) to assess the degree of sedation or agitation presented by the patient. It is a 10-point scale, very intuitive in its description since the positive values indicate agitation and the negative values are used to quantify sedation, in such a way that level 0 corresponds to a calm and awake patient, level 4

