10 STATISTICAL ANALYSIS

A statistical analysis will be carried out after the development of a basis for the collection of patient data, by protocol and in accordance with the principle of "intention to treat".

After identifying extreme data, a subsequent analysis will be carried out to assess the normality of the variables. All variables related to efficacy and safety will be analyzed for both treatment arms.

Categorical variables shall be expressed in percentages and number of observations. Continuous variables shall be expressed as mean and standard deviation or medians and interquartile ranges (25 – 75) and/or minimum and maximum. Relative risks of the estimated effect and its 95% confidence intervals shall be calculated and presented. For the comparison of categorical variables, the Chi-square test or the Fisher's test will be used, when necessary. For the comparison of the continuous variables, the Student's "t" test or Mann-Whiteney U test will be used for both simple and paired data, or other non-parametric tests, if necessary. Multivariate and survival analyses will be used to determine whether the association between the intervention and theprimary (or secondary) objective is free from confusion. Covariates in each model will be considered as those that in the univariate analysis show a value of p < 0.1

All analyses will be performed with hypothesis contrast of 2 tails and a significance level of 5%.

The statistical program used will be SPSS[®] 21.0.

Intermediate analyses are not planned except those indicated by the Safety Committee in order to safeguard the health of patients included in the study.

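### Sections 6.5 and 7.2 III conflict on whether withdrawn patients keep daily CAM assessment to day 4, and section 10 has no rule for the missing data

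*Combined protocol and SAP*

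**What the plan says.** Section 5.1 defines the primary variable as the number of delirium cases over the total number of patients in the first four postoperative days, diagnosed by CAM. The rules on who is assessed, and until when, are these:

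- **Section 6.4, item 2a** lists as a reason for withdrawal "Admission to critical care units for postoperative complications". Other reasons are patient choice, QTc prolongation, safety and non-compliance.
- **Section 6.5**: "In the case of retired patients, follow-up will be done until the date of withdrawal", plus a premature withdrawal visit.
- **Section 7.2 V** applies to patients who "prematurely and permanently stop treatment, must complete the premature withdrawal visit". CAM is listed once among its procedures. On the timing of this visit the section says: "which will take place in the following 24-48 hours from the time the withdrawal is known". The Figure 1 column headed "Retirada prematura" agrees. Neither place lists mortality or SF-36.
- **Section 7.2 III**: "A daily personal clinical visit will be made to all randomized patients during the first four days of the postoperative period", or until earlier discharge, with CAM at each visit.
- **Section 8.2**: "The assessment of the response will be carried out daily in both study groups, during the first 4 days of admission", or until discharge.
- **Section 10**: the analysis is to be "by protocol and in accordance with the principle of" intention to treat. Neither set is called primary. There is no rule for a missing CAM. Survival analyses are mentioned without a censoring rule.

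**The concern.** Two readings are open. On one, 6.5 is an exception to 7.2 III, and daily CAM ends when a patient is withdrawn. On the other, 7.2 V only adds a visit to the daily schedule, and nothing is lost. Staff who follow the first reading lose primary-outcome data that staff who follow the second collect, and the lost days cannot be recovered later.

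For critical-care transfers the loss is likely to be informative on the protocol's own evidence. Section 3 cites delirium of up to 80% in patients requiring critical care. The entry risk score in 6.1 gives critical-care admission 3 points, and every other item 1 or 2. The protocol states no such link for the other withdrawal reasons.

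If withdrawal differs between arms, counting missed patients as non-cases favours the arm with more withdrawals. Excluding them favours that arm only if their delirium risk is above average.

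**Working it through.** **The plan's own figure.** This point does not dispute the sample size. A pooled two-proportion calculation (two-sided 5%, 80% power) for 25% against 13% gives 167 per arm. Then 167/0.95 = 175.8, so 176 per arm and 352 in total, against the stated 350. With 22.5% against 10.5% and a continuity correction it gives 166 per arm, then 175, and exactly 350.

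**Days without a CAM if 6.5 is followed.** Suppose withdrawal falls on day *d*, after that day's CAM, and the visit on day *d*+1 or *d*+2. If the visit falls by day 4, the days left are 4 − *d* − 1.

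| Withdrawal day | Assessment days without a CAM |
|---|---|
| 0 | 3 |
| 1 | 2 |
| 2 | 1 |
| 3 | 0 (visit day 4) or 1 (visit day 5) |
| 4 | 0 |

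**Effect on the comparison.** From the documents: 175 per arm, 5% expected losses and 20–25% incidence (6.3), a two-sided 5% test (section 10), and up to 80% delirium in critical care (section 3). Assumed, because the documents give no values: no true effect, the split of withdrawals between arms, a delirium risk *r* of 50–80% in withdrawn patients, and the share *c* of their delirium that is caught. With *p* the true rate in both arms and *w* the share withdrawn:

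- counted as non-cases unless caught: observed rate = *p* − *w r* (1 − *c*)
- excluded: observed rate = (*p* − *w r*)/(1 − *w*), with *n* = 175(1 − *w*)
- type I error = Φ((δ − 1.96 s₀)/s₁) + Φ((−δ − 1.96 s₀)/s₁), where δ is the false difference, s₀ the pooled and s₁ the unpooled standard error.

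One case in full: *p* = 0.25, *w* = 1/30 against 2/30 (mean 5%; about 6 against 12 patients), *r* = 0.8, *c* = 0. The observed rates are 0.25 − 0.0267 = 22.33% and 0.25 − 0.0533 = 19.67%, so δ = 2.67 points. With s₀ = 0.04354 and s₁ = 0.04352, the two terms are Φ(−1.35) = 0.089 and Φ(−2.57) = 0.005, together 0.094.

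All cases at *p* = 0.25 (false difference in percentage points; type I error in parentheses):

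| Withdrawn | Handling | *r* = 50% | *r* = 80% |
|---|---|---|---|
| 3.3% vs 6.7% | half caught | 0.83 (0.054) | 1.33 (0.060) |
| 3.3% vs 6.7% | excluded | 0.92 (0.054) | 2.03 (0.073) |
| 3.3% vs 6.7% | none caught | 1.67 (0.066) | 2.67 (0.094) |
| 5% vs 10% | half caught | 1.25 (0.059) | 2.00 (0.074) |
| 5% vs 10% | excluded | 1.46 (0.061) | 3.22 (0.110) |
| 5% vs 10% | none caught | 2.50 (0.088) | 4.00 (0.159) |

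The rows with none caught are upper bounds, because a withdrawal CAM is scheduled. At *p* = 0.20 with 3.3% against 6.7%, the three handlings give 0.055–0.062, 0.058–0.084 and 0.069–0.104. Exact enumeration of the uncorrected chi-square test agrees within 0.002.

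**Where the bias is small or absent.** With equal withdrawal and equal risk in both arms it is zero. With withdrawn patients at average risk (*r* = 25%, *p* = 0.25) and the 3.3% against 6.7% split, exclusion gives zero bias, half caught gives 0.051 and none caught gives 0.054.

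**The case against.** The strongest reply is that 6.5 is written for withdrawn patients and so overrides the general schedule in 7.2 III. That would make this a debatable design choice rather than a contradiction. The reading is fair, but the text does not state it, and 7.2 III covers all randomised patients without exception. Under that reading, the data loss is the intended rule.

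The opposite reply is that the protocol already separates stopping capsules from stopping visits. Section 7.3 stops study medication when delirium develops in the first three days, and 7.2 III continues daily visits for those patients. This is true, but they are already counted as cases. It leaves open what happens to patients withdrawn without delirium.

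Several points limit the size, and they stand:

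- The CAM caregiver question looks back 24 hours, and the withdrawal visit records any delirium that has developed. Some delirium between withdrawal and that visit is therefore recoverable.
- High risk is supported only for critical-care transfers, and the 80% is an upper figure. Nothing in the documents suggests that withdrawal will differ by arm.
- Deaths are still captured as serious adverse events to day 28. A visit at 24–48 hours could not measure 28-day outcomes, so their absence from it does not show that they are dropped. What remains is that 6.5 does not say whether the 28-day contact, and with it SF-36, is kept.
- The gaps in section 10 exist whatever 6.5 says. They matter here because the analysis plan cannot settle what the visit schedule leaves open.

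**Conclusion.** The concern holds and should be fixed. The conflict between 6.5 and 7.2 III/8.2 is certain from the text, it affects the primary outcome, and section 10 does not resolve it. The effect on the result is not known. At an average withdrawal equal to the stated 5% losses, an assumed two-fold imbalance and 50–80% risk give a type I error of 0.054–0.060 if half the delirium is caught. It is 0.054–0.073 if these patients are excluded, and at most 0.066–0.094 if none is caught. At 5% against 10% withdrawn, the corresponding figures are 0.059–0.074, 0.061–0.110 and 0.088–0.159. All of these rest on an imbalance between arms that may not occur. No loss of power is claimed.

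**What to change.** Reconcile 6.4, 6.5, 7.2 III, 7.2 V and Figure 1 by distinguishing a patient who stops study capsules from one who leaves the study. Unless consent is withdrawn, continue RASS and CAM to postoperative day 4 or discharge, and keep the discharge visit and the 28-day mortality and SF-36 contact. The rules for stopping capsules are not touched.

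In section 10:

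- make all randomised patients, analysed as randomised, the primary set, with per-protocol as supportive;
- prespecify how a missing CAM is handled, and the censoring rule if survival analysis is used;
- add a sensitivity table that varies the delirium risk of missing patients separately by arm, from the observed rate up to 80%.

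The cost is protocol wording, a few more bedside visits in the same hospital, and one 28-day contact per stopped patient. One gap remains. A patient who stays at RASS −4 or −5 will still lack a CAM, because 8.2 only repeats the assessment, so the missing-CAM rule is needed in any case.

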- Age: 70-79 years: 1 point; >80 years: 2 points
- Physical activity: need for assistance, not self-sufficient: 2 pointss
- Alcoholism: 1 point
- Hearing deficit: 1 point
- History of delirium: 2 points
- Urgent surgery: 1 point
- Non-laparoscopic surgery: 2 points
- Admission to Critical Care Units: 3 points
- C-Reactive Protein (CRP) value > 10 mg/dL: 1 point

The necessary sample size will be 350 patients, 175 patients per branch (control and experiment).

1.16DURATION OF PROCESSING

The duration of the treatment will be three days included in the early postoperative phase. Quetiapine will be administered orally to the patients of the experimental group 60 minutes after arrival at Resuscitation/Post-Anesthetic Recovery Unit and thereafter every 12 hours until the 3rd postoperative day. Subjects in the control group will be given placebo in the same time and form as subjects in the experimental group.

1.17 CLINICAL TRIAL SCHEDULE.

The total duration of the clinical trial will be approximately 3 years. They include the period for approvals and coordination of the project, period of recruitment and monitoring, period or analysis of results and a final period for the publication of results.

1.18COLLABORATING INVESTIGATORS OF THE TRIAL

[name] [name]. Head of Service Anesthesiology, resuscitation and pain management. C.A.U.S.A - Biomedical Research Institute of Salamanca (IBSAL)

[name] [name]. Medical assistant to the Anesthesiology, Resuscitation and Pain Treatment Service. C.A.U.S.A. - Biomedical Research Institute of Salamanca (IBSAL).

[name] [name]. Medical assistant to the Anesthesiology, Resuscitation and Pain Treatment Service. C.A.U.S.A.

[name] [name]. Medical assistant to the Anesthesiology, Resuscitation and Pain Treatment Service. C.A.U.S.A.

[name] [name]. Head of section of the Anesthesiology, Resuscitation and Pain Treatment Service. C.A.U.S.A.

[name] [name]. Medical assistant to the Anesthesiology, Resuscitation and Pain Treatment Service. C.A.U.S.A.

[name]. Medical assistant to the Anesthesiology, Resuscitation and Pain Treatment Service. C.A.U.S.A.

[name] [name]. Assistant Physician Anesthesiology, Resuscitation and Pain Treatment Service. C.A.U.S.A.

[name]. Medical assistant to the Anesthesiology, Resuscitation and Pain Treatment Service. C.A.U.S.A.

[name]. Medical assistant to the Anesthesiology, Resuscitation and Pain Treatment Service. C.A.U.S.A.

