
Given the importance of this condition, its prevalence and its consequences, we think that prophylaxis in the population at risk (patients >65 years postoperative for non-cardiac surgery) during the first 72 hours after surgery with small doses of quetiapine can provide great benefits (decreased incidence, decreased duration and severity delirium) with a low level of risk since it has a favorable safety profile.

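### The only scheduled on-treatment ECG has an earliest time but no latest time, so it can fall after the last capsule, too late for the QTc withdrawal rule to spare a dose

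*Combined protocol and SAP*

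**What the plan says.** Dosing (section 7.1): the first capsule "will be administered 60 minutes after arrival at the resuscitation unit and every 12 hours thereafter for the first 3 postoperative days". All medication is dispensed at once, "in a bottle containing the 6 corresponding capsules". Section 1.16 words the end of dosing as "thereafter every 12 hours until the 3rd postoperative day", and section 3 speaks of prophylaxis "during the first 72 hours after surgery".

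ECG (section 7.2, postoperative visits): "ECG and QTc measurement (after administration of the 4th dose". Figure 1 marks an ECG at the selection visit and at 3-post, and at no other visit. Visits "will be listed in corresponding to the postoperative day: visit 1st day post, visit 2nd day post", and so on to day 4. No section says where day 1 begins.

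Stopping rule (section 6.4, criterion 2b): "Significant prolongation of the QTc interval: prolongation greater than 60 miliseconds or QTc greater than 500 msec", or ventricular tachycardia or torsades. Criterion 2c allows withdrawal whenever treatment is no longer safe.

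Analysis: section 5.1 makes the QTc increase on the control ECG a safety variable. Section 10 compares continuous variables by t-test or Mann-Whitney and picks model covariates by univariate p < 0.1.

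**The concern.** The protocol has a written QTc stopping rule and one scheduled ECG that can inform it during treatment. That ECG has a lower limit (dose 4) and no upper limit. A site that follows section 7.2 and Figure 1 to the letter may take it after the sixth capsule. It would then still supply the QTc safety variable, but it could no longer stop a dose. What is at stake is whether the rule can act on the scheduled reading. Efficacy inference is not involved.

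**Working it through.** **Inputs.** First dose 1 h after arrival, 12 h interval, six capsules (section 7.1). ECG after dose 4, marked at 3-post (section 7.2, Figure 1). The documents give no arrival or visit hours. I assume arrivals on the hour from 01:00 to 24:00 and visits on the hour from 08:00 to 16:00, unweighted: 24 x 9 = 216 combinations.

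**The plan's own figure.** 6 x 25 mg = 150 mg, as section 5.4 states.

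**Dose times.** Dose k falls at 1 + 12(k - 1) h after arrival: 1, 13, 25, 37, 49, 61 h.

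**Which day count fits?**
- 24-hour blocks from arrival: doses fall in blocks 1, 1, 2, 2, 3, 3. This agrees with sections 1.16, 3, 5.4 and 7.1.
- Surgery as day 1: dose 6, at arrival clock hour + 61, passes 72 h when arrival is after 11:00. It then falls on day 4, against section 7.1.
- Surgery as day 0: dose 6 falls on day 2 when arrival is before 11:00, against section 1.16. The first dose also usually precedes postoperative day 1.

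Blocks therefore fit best.

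**Capsules already given at 3-post.** For arrival hour h and visit hour v, 3-post is the first v at or after h + 48 (blocks), 72 + v (day 0) or 48 + v (day 1).

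| Count | 3 given | 4 | 5 | 6 | All six given | Four or five given |
|---|---|---|---|---|---|---|
| Blocks (48-72 h) | 0 | 9 | 108 | 99 | 99/216 = 46% | 117/216 = 54% |
| Day 0 | 0 | 0 | 15 | 201 | 201/216 = 93% | 15/216 = 7% |
| Day 1 | 15 | 102 | 93 | 6 | 6/216 = 3% | 195/216 = 90% |

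The block figure can be checked without a grid. Between 48 and 72 h, two capsules remain for 1 h (48-49), one for 12 h (49-61) and none for 11 h (61-72); 11/24 = 46%. With arrivals 09:00-24:00 only (144 combinations), all six have been given in 93 (65%), 129 (90%) and 0 for the three counts.

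**Does a capped window work?** Doses 4 and 6 bound 37-61 h, which is 24 h long, so it holds 8 hours between 08:00 and 16:00 for every arrival time. The narrower window before dose 5 (37-49 h) holds none for arrivals 03:00-07:00. Such arrivals are possible because urgent surgery is eligible (section 6.1: "Urgent surgery: 1 point"). Under blocks, 3-post alone (48-61 h) holds none for arrivals 16:00-19:00, so 2-post must also be allowed. With both visits allowed, every count leaves usable time. The tightest case is day 1 with arrival at 24:00: the window runs from 61 to 85 h on the clock, which leaves 13:00-16:00 on 3-post.

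**Likely numbers.** Annex 7 lists QT prolongation as uncommon, and section 5.4 defines that class as 1/1,000 to under 1/100. Over 175 quetiapine patients this is 175 x 0.001 = 0.2 to 175 x 0.01 = 1.75. The class covers any QT prolongation and is not specific to older surgical patients, so this indicates scale only.

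**QTc comparison.** With equal variance s² at both visits and correlation rho, the increase has variance 2s²(1 - rho) and the ANCOVA residual s²(1 - rho²). The ratio is (1 + rho)/2: 0.65, 0.75 and 0.85 at assumed rho of 0.3, 0.5 and 0.7.

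**The case against.** The strongest reply is that the schedule is coherent as written. Under 24-hour blocks dose 4 closes day 2, so an ECG after it at 3-post makes sense, and at least one capsule can still be stopped in 54% of the grid. The counts also assume that treatment continues. Section 7.3 stops study drug if delirium develops in the first three days, section 6.4 withdraws patients admitted to critical care for complications, and some patients go home early. The withdrawal rule applies throughout the study and is not tied to this ECG. Finally, reading the QTc near full exposure is defensible for a safety variable.

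Most of this stands and limits the point. The shares describe patients still on treatment, and the text and Figure 1 do not contradict each other. But on the best-fitting count nearly half of the combinations are still too late. A reading after four doses is already allowed by section 7.2, so a cap does not introduce a new kind of measurement.

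A reader might infer that the scheduled ECG nearly always comes too late, from the 93%. That figure needs surgery to be day 0, which fits the dosing statements poorly. A reader might also infer that the stopping rule cannot work at all. Unscheduled ECGs, ventricular arrhythmia and criterion 2c can all still end treatment.

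**Conclusion.** The point holds, and it is minor. Followed as written, the only scheduled on-treatment ECG can come after the last capsule: in about 46% of assumed combinations on the best-fitting day count, with 3% and 93% on the two calendar counts. These shares rest on assumed, unweighted arrival and visit hours and apply to patients still receiving study drug.

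Few patients are likely to meet the QTc criterion. No firm bound on doses spared can be given, because the label class neither matches the 60/500 msec thresholds nor describes this population. The primary analysis is unaffected. It would also be wrong to infer a biased QTc comparison: the timing rule is the same in both randomized, masked arms, so variable timing by itself adds noise.

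The ANCOVA suggestion is a separate, free improvement. The protocol sets no precision target for QTc, so it does not repair a shortfall.

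**What to change.** In section 7.2, and as a footnote to the ECG row of Figure 1, require the existing ECG after dose 4 and before dose 6 (37-61 h after arrival), preferably before dose 5. It is done at the 2-post or 3-post visit, whichever falls in the window, in patients still receiving study drug. Because the window is tied to doses, it works under any day count.

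In section 10, add one sentence: control QTc is compared between arms by ANCOVA with selection-visit QTc as a prespecified covariate, in place of an unadjusted test of the increase.

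Cost: one phrase, one footnote and one sentence, with no extra ECG. The downside is that the QTc result reflects four or five doses instead of six.
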